4.4.2 Exclusion Criteria

Subjects presenting with any of the following will not participate in the study:

1. Non-plaque-type psoriasis (eg, pustular, erythrodermic, and guttate psoriasis).
2. Drug-induced psoriasis (ie, new onset or current exacerbation from beta-blockers, calcium channel blockers, or lithium).
3. Spontaneously improving or rapidly deteriorating plaque psoriasis.
4. Comorbid psoriatic arthritis not amenable to treatment with nonsteroidal anti-inflammatory drugs (NSAIDs).
5. Treatment with any biologic agent for plaque psoriasis.
6. Failed 2 or more systemic treatments for plaque psoriasis.
7. Received phototherapy or prolonged sun exposure or use of tanning booth or other ultraviolet light source within 4 weeks prior to initiating screening procedures.
8. Received systemic drug therapy (non-biologic) for plaque psoriasis or any other systemic medications that could affect psoriasis or its evaluation (PASI or static IGA), including but not limited to oral or injectable corticosteroids, retinoids, sulfasalazine, within 4 weeks of initiating screening procedures.
9. Received topical medication that could affect psoriasis or its evaluation (PASI or static IGA), including but not limited to corticosteroids, retinoids, topical vitamin D derivatives, pimecrolimus, tacrolimus, calcipotriene, within 2 weeks of initiating screening procedures.
10. Received immunosuppressant agents (eg, cyclosporine, azathioprine, methotrexate) within 8 weeks of initiating screening procedures.

LYC-30937

Clinical Protocol LYC-30937-2003

Issue Date: 30 August 2016

11. Known mitochondrial disorder.
12. Any of the following laboratory abnormalities:
 - a liver function tests > 1.5 x the upper limit of normal (ULN) or direct bilirubin > 1.5 x ULN
 - b hemoglobin < 8.5 g/dL (international system units [SI]: < 85 g/L)
 - c neutrophils $< 1500/\text{mm}^3$ (SI: $< 1.5 \times 10^9/\text{L}$)
 - d white blood cell (WBC) count $< 3000/\text{mm}^3$ (SI: $< 3.0 \times 10^9/\text{L}$)
 - e platelets $< 80000/\text{mm}^3$ (SI: $80 \times 10^9/\text{L}$)
 - f serum creatinine > 1.4 mg/dL for women or > 1.6 mg/dL for men
13. Pregnancy, lactation, or a positive serum beta human chorionic gonadotropin (hCG) measured at screening. Female subjects should not be planning to become pregnant while enrolled in the study.

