^a Demography includes smoking status, drug and alcohol consumption, and date of chronic plaque-type psoriasis diagnosis.

^b HbsAG, HCV antibodies, and HIV-1/2 antibodies.

^c Post-menopausal is defined as having no menses for ≥ 6 months prior to screening and a serum FSH level > 25 mIU/mL at screening.

^d Vital signs will be collected after the subject has been sitting quietly for ≥ 5 minutes and include blood pressure (systolic and diastolic), heart rate, respiratory rate, and temperature.

^e Chemistry panel includes: glucose, calcium, sodium, albumin, total protein, potassium, bicarbonate, chloride, BUN, creatinine, lactate, LDH, ALT, AST, reflexive bilirubin (total, direct, indirect), ALP, cholesterol, triglycerides, CPK, hsCRP, HDL, and LDL.

LYC-30937

Clinical Protocol LYC-30937-2003

Issue Date: 30 August 2016

- ^f Hematology Panel includes: platelets, WBCs with differential if abnormal (% and absolute counts), hematocrit, RBCs, hemoglobin, MCV, MCHC, and MCH.
- ^g Urinalysis (dipstick) includes: color, appearance, specific gravity, leukocyte esterase, pH, protein, glucose, ketones, blood, and nitrites. Microscopic urinalysis will be performed on samples with abnormal blood, leukocyte esterase, protein, and nitrate.
- ^h All subjects will have one blood sample collected at Week 8 (any time post study drug dose) to measure plasma LYC-30937 concentration.
- ⁱ AEs will be assessed after the informed consent is signed.
- ^j Photographs will be taken at randomization (pre-dosing) and at Week 12 in a subset of subjects.
- ^k Optional skin biopsy will be collected at Week 8 in a subset of approximately 6 consenting subjects. Biopsy collection instructions will be included in a separate document. This tissue will be assayed for concentration of LYC-30937.
- ^l Note that confirmation of moderate plaque-type psoriasis is determined at both Screening and Visit 2 (baseline, prior to first dose).
- ^m Site will telephone subjects the day after randomization visit to remind them to take study drug in the morning after fasting overnight and to wait approximately 1 hour before eating a meal.

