6.2.1 Visit Procedure Guidelines

No study-related procedures will be performed until each subject has been completely informed of the details of the study including its nature, risks, and procedures, and has signed and dated IRB/IEC-approved informed consent document (ICD). A subject who satisfies all eligibility criteria during the screening visit may proceed to the next visit.

A laboratory test (eg, alanine aminotransferase [ALT], aspartate aminotransferase [AST], platelets) or procedure that does not meet eligibility criteria can be repeated once at the discretion of the investigator in order to determine eligibility. A subject who does not satisfy all entry requirements that can be assessed during the screening phase will require no further visits and will be identified as a screen failure in the source documents and CRFs.

Re-screening of subjects initially not meeting all selection criteria may be allowed once after consultation with the sponsor.

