6.4.4 Laboratory Assessments

Laboratory assessments will be performed at the time points indicated in the schedule of assessments (Table 1) and will be evaluated by a central laboratory.

The PI at the site must assess the clinical significance of all laboratory values outside the laboratory reference ranges. All laboratory abnormalities considered to be clinically significant by the PI should be repeated. Confirmed, clinically significant laboratory abnormalities should be further evaluated by the PI and captured as an AE.

Chemistry Panel Sample

The chemistry panel includes: glucose, calcium, sodium, albumin, total protein, potassium, bicarbonate, chloride, blood urea nitrogen (BUN), creatinine, lactate, lactate dehydrogenase (LDH), alanine aminotransferase (ALT), aspartate aminotransferase (AST), reflexive bilirubin (total, direct, indirect), alkaline phosphatase (ALP), cholesterol, triglycerides, creatine phosphokinase (CPK), high sensitivity C-reactive protein (hsCRP), high density lipoprotein (HDL), and low density lipoprotein (LDL).

Hematology Panel Sample

The hematology panel includes: platelets, WBCs with differential if abnormal (% and absolute counts), hematocrit, red blood cells (RBCs), hemoglobin, mean corpuscular volume (MCV), mean corpuscular hemoglobin concentration (MCHC), and mean corpuscular hemoglobin (MCH).

LYC-30937

Clinical Protocol LYC-30937-2003

Issue Date: 30 August 2016

Urine Sample (Dipstick)

The urinalysis test includes: color, appearance, specific gravity, leukocyte esterase, pH, protein, glucose, ketones, blood, and nitrates. Microscopic urinalysis will be performed on samples with abnormal blood, leukocyte esterase, protein, and nitrate. This test will be evaluated by dipstick at the central laboratory.

Childbearing Potential Evaluation and Pregnancy Tests

Serum FSH in postmenopausal female subjects and a serum hCG (pregnancy test) in premenopausal females will be evaluated at the central lab at screening.

Urine pregnancy tests for female subjects of childbearing potential will be performed at the time points indicated in the schedule of assessments (Table 1).

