6.6 Clinical Laboratory

Clinical labs are reported for hematology, chemistry, and urinalysis and they include the following parameters:

- **Chemistry:** glucose, calcium, sodium, albumin, total protein, potassium, bicarbonate, chloride, blood urea nitrogen (BUN), creatinine, lactate, lactate dehydrogenase (LDH), alanine aminotransferase (ALT), aspartate aminotransferase (AST), reflexive bilirubin (total, direct, indirect), alkaline phosphatase (ALP), cholesterol, triglycerides, creatine phosphokinase (CPK), high sensitivity C-reactive protein (hsCRP), high density lipoprotein (HDL), and low density lipoprotein (LDL).
- **Hematology:** platelets, white blood cells (WBCs) with differential if abnormal (% and absolute counts), hematocrit, red blood cells (RBCs), hemoglobin, , mean corpuscular volume (MCV), mean corpuscular hematocrit concentration (MCHC), and mean corpuscular hematocrit (MCH).

- **Urinalysis:** color, appearance, specific gravity, leukocyte esterase, pH, protein, glucose, ketones, blood, and nitrates. Microscopic urinalysis will be performed on samples with abnormal blood, leukocyte esterase, protein, and nitrate.

Hematology and chemistry are collected at Screening, Week 2, Week 4, Week 8, Week 12, and at Week 14 (follow-up). Values and change from baseline will be summarized by visit, for the end of treatment visit, and for the overall worst value post-baseline (which includes unscheduled visits), within each treatment group. Appendix 5 provides the directionality of the worst values for each laboratory parameter.

Urinalysis is collected at Screening and Week 12. Results will be listed by subject.

Out-of-range values will be assessed through shift tables. Each lab value will be assessed as low, normal or high based on the normal ranges provided by the central lab. Frequencies of each combination of shifts from baseline to post-baseline visits will be provided by treatment group for hematology and chemistry lab parameters only. Separate by subject listings will also be produced and out-of-range values will be flagged.

Over the course of the study, there may be some labs tests performed that were not mentioned in the protocol. These tests will not be summarized but will be included in the listings and flagged as non-protocol tests.

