- ^c Post-menopausal is defined as having no menses for ≥ 6 months prior to screening and a serum FSH level > 25 mIU/mL at screening.
- ^d Vital signs will be collected after the subject has been sitting quietly for ≥ 5 minutes and include blood pressure (systolic and diastolic), heart rate, respiratory rate, and temperature.
- ^e Chemistry panel includes: glucose, calcium, sodium, albumin, total protein, potassium, bicarbonate, chloride, BUN, creatinine, lactate, LDH, ALT, AST, reflexive bilirubin (total, direct, indirect), ALP, cholesterol, triglycerides, CPK, hsCRP, HDL, and LDL.
- ^f Hematology Panel includes: platelets, WBCs with differential if abnormal (% and absolute counts), hematocrit, RBCs, hemoglobin, MCV, MCHC, and MCH.

LYC-30937-EC
Statistical Analysis Plan, V1.0

- ^g Urinalysis (dipstick) includes: color, appearance, specific gravity, leukocyte esterase, pH, protein, glucose, ketones, blood, and nitrites. Microscopic urinalysis will be performed on samples with abnormal blood, leukocyte esterase, protein, and nitrate.
- ^h All subjects will have one blood sample collected at Week 8 (any time post study drug dose) to measure plasma LYC-30937 concentration.
- ⁱ AEs will be assessed after the informed consent is signed.
- ^j Photographs will be taken at randomization (pre-dosing) and at Week 8 in a subset of subjects.
- ^k Optional skin biopsy will be collected at Week 8 in a subset of approximately 6 consenting subjects. Biopsy collection instructions will be included in a separate document. This tissue will be assayed for concentration of LYC-30937.
- ^l Note that confirmation of moderate plaque-type psoriasis is determined at both Screening and Visit 2 (baseline, prior to first dose).
- ^m Site will telephone subjects the day after randomization visit to remind them to take study drug in the morning after fasting overnight and to wait approximately 1 hour before eating a meal.

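### The hematology panel orders a white-cell differential only when something is abnormal, so it does not guarantee the neutrophil count that exclusion 12c needs, and the differential summaries would rest on trigger-selected samples

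*Protocol*

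**What the plan says.** Four passages define the hematology panel, and all make the differential conditional:

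- Protocol 6.2, Table 1, footnote f: "Hematology Panel includes: platelets, WBCs with differential if abnormal (% and absolute counts), hematocrit, RBCs, hemoglobin".
- Protocol 6.4.4: "The hematology panel includes: platelets, WBCs with differential if abnormal (% and absolute counts), hematocrit".
- SAP 6.6: "white blood cells (WBCs) with differential if abnormal (% and absolute counts), hematocrit".
- SAP Appendix 1, footnote f: "Hematology Panel includes: platelets, WBCs with differential if abnormal (% and absolute counts), hematocrit, RBCs, hemoglobin, MCV, MCHC, and MCH".

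None names the triggering result or its limit, and none treats screening differently. For urinalysis, by contrast, footnote g lists the dipstick results that lead to microscopy.

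Three parts of the plan use a differential:

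- **Eligibility.** Protocol 4.4.2 excludes neutrophils below 1500/mm³ (12c) and, separately, total WBC below 3000/mm³ (12d). Protocol 6.2.1 adds: "A subject who satisfies all eligibility criteria during the screening visit may proceed to the next visit".
- **Monitoring.** In Protocol 6.4.6, eosinophilia above 5% is one of the features in a criterion for withholding study drug.
- **Analysis.** SAP 6.6 plans hematology values and change from baseline by visit, at end of treatment and for the worst post-baseline value, plus shift tables. SAP Appendix 5 sets a worst-value direction for neutrophils, lymphocytes, monocytes, eosinophils and basophils.

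The only scheduled hematology draw before dosing is at screening; the later ones are at Weeks 2, 4, 8, 12 and 14. Under SAP 5.4 and 5.7 a missing baseline is not imputed, and the subject drops out of change from baseline for that parameter.

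**The concern.** A criterion that applies to every screened subject needs a measurement that every screened subject has. The panel does not order it for all of them, so whether 12c is checked would depend on an unstated trigger or on a site or laboratory going beyond the panel text.

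The second issue is selection. If a differential exists only when another result is abnormal, the arm summaries for the five cell types describe the triggered samples, not the arms. Change from baseline and shift tables are thinner still, because they also need a differential that was triggered at screening.

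The lymphocyte rows have some relevance, since Protocol 2.2 describes the drug as inducing apoptosis in metabolically sensitive lymphocytes. That relevance is limited. Protocol 1.0 says the effect differs between chronically activated and normal lymphocytes, which a routine count does not separate.

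**Working it through.** There is no stated figure in the plan to reproduce. The finding rests on the text; the arithmetic shows its scale.

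**Step 1. Does 12d cover 12c?** Inputs: 1500/mm³ (12c) and 3000/mm³ (12d), Protocol 4.4.2. A subject meets 12c when the neutrophil fraction is below 1500 / WBC.

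| WBC per mm³ (all pass 12d) | Fraction below which 12c is met |
|---|---|
| 3000 | 1500/3000 = 50.0% |
| 4000 | 1500/4000 = 37.5% |
| 4500 | 1500/4500 = 33.3% |
| 5000 | 1500/5000 = 30.0% |

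Example: 4500 × 0.30 = 1350/mm³. The subject passes 12d and meets 12c, so 12d cannot stand in for 12c.

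**Step 2. How many subjects would the summaries contain?** Inputs: 30 subjects, 20 active and 10 placebo (Protocol 8.1), and five scheduled post-baseline draws (SAP 6.6, taking Week 14 as included in the worst value). The probability p that one sample triggers a differential is not in the documents; 0.05 to 0.20 is an assumption. Expected subjects of 30:

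| Summary | Formula | p = 0.05 | p = 0.10 | p = 0.20 |
|---|---|---|---|---|
| Values at one visit | 30p | 1.5 | 3 | 6 |
| Worst post-baseline value, independent triggers | 30[1 − (1 − p)^5] | 6.8 | 12.3 | 20.2 |
| Change or shift at one visit, independent triggers | 30p² | 0.08 | 0.30 | 1.2 |
| Change to worst value, independent triggers | 30p[1 − (1 − p)^5] | 0.34 | 1.23 | 4.03 |
| Any row, if the same subjects always trigger | 30p | 1.5 | 3 | 6 |

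By arm, values at one visit come from 20p = 1 to 4 active and 10p = 0.5 to 2 placebo subjects. Repeated counts in one subject are correlated, so the truth should lie between the independent rows and the last row.

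**Step 3. Does selection distort the values?** This is an illustration with assumed inputs and no drug effect: WBC normal with mean 7000 and SD 1800, neutrophil fraction normal with mean 0.58 and SD 0.09, and the trigger taken as a WBC outside the laboratory range. With a range of 4000 to 11000, about 6% of samples trigger. Their mean neutrophil count is about 2940 (SD about 2120), against 4060 (SD 1230) in all samples. With 3500 to 10500 the mean does not move, but the SD rises to about 2570. The direction and size of the distortion therefore depend on the trigger, which the documents leave undefined.

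**The case against.** The strongest reply is that nothing here contradicts anything else. Exclusion 12c and Protocol 6.2.1 themselves require the neutrophil criterion to be satisfied, the panel text does not forbid the count, and Protocol 6.4.4 sends samples to a central laboratory that may report a differential on every sample. This stands in part. A reader might infer that 12c will go unchecked or that ineligible subjects will be enrolled, and the documents do not support that. They show an incomplete panel that must be reconciled with 12c, not two rules that cannot both be followed. But no passage says that the laboratory reports differentials routinely.

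Second, missed cases may be very rare. In the Step 3 model, 2% to 9% of neutrophil counts below 1500 come with an in-range WBC, for assumed lower limits from 4500 down to 3500. That is about 0.005 to 0.03 subjects per 30 screened. Widening the SD of the fraction to 0.12 gives about 0.07 to 0.14. These are assumed distributions, not trial data, but they give no ground for claiming a large effect.

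Third, SAP 6.6 states the condition itself, SAP 5.4 and 5.7 make the available-data rule explicit, and Appendix 5 gives only a direction for values that exist. So it would be wrong to infer that the summaries cannot be run: by-visit and worst values can be run on whatever is available. What is missing is any statement that those rows cover a selected subset.

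Finally, a reader might infer that a harmful fall in lymphocytes would be hidden. The documents do not support that either. Protocol 2.3.3 reports no generalized immunosuppression in rats and monkeys dosed for up to 28 days, although its account of the 91-day studies gives no blood-count result.

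**Conclusion.** The concern holds as a gap that should be reconciled. As written, the panel does not deliver the count that 12c needs from every screened subject; the eosinophilia element in Protocol 6.4.6 has the same dependence; and the summaries for five cell types would rest on samples selected by the triggering result. These conclusions need no assumed rate.

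The consequence is limited. SAP 5.1 and 6.4 keep the safety analyses descriptive, the primary endpoint is unaffected, and no lymphocyte limit governs eligibility or withholding. Neither the trigger rate nor the frequency of missed 12c cases is in the documents. The subject counts in Step 2 rest on the assumed 5% to 20% and on the two dependence extremes, so they show a range and are not a forecast.

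**What to change.** Delete the words 'if abnormal' after 'differential' in Protocol Table 1 footnote f, Protocol 6.4.4, SAP 6.6 and SAP Appendix 1 footnote f, so that percentages and absolute counts are reported for every scheduled hematology sample. Every screened subject then has the count for 12c, every randomized subject can have a baseline, and the post-baseline rows are no longer trigger-selected. No clinical threshold changes.

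The cost is a protocol amendment with prospective IRB/IEC approval (Protocol 9.2), two SAP wording changes, and a per-sample laboratory charge whose amount is not in the documents. The charge covers up to 30 × 6 = 180 scheduled samples in randomized subjects, plus one for each screen failure. No visit or draw is added.

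The minimum alternative is an unconditional differential at screening, a stated trigger for later visits, and a note in SAP 6.6 and Appendix 5 that the post-baseline differential rows cover trigger-selected samples only. It costs less in laboratory charges but still needs the amendment.

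A separate minor correction, which adds no weight to this point: SAP Appendix 5 takes the highest HDL as the worst value, so that summary picks the least adverse reading. Change the direction to lowest.

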6.2.1 Visit Procedure Guidelines

No study-related procedures will be performed until each subject has been completely informed of the details of the study including its nature, risks, and procedures, and has signed and dated IRB/IEC-approved informed consent document (ICD). A subject who satisfies all eligibility criteria during the screening visit may proceed to the next visit.

A laboratory test (eg, alanine aminotransferase [ALT], aspartate aminotransferase [AST], platelets) or procedure that does not meet eligibility criteria can be repeated once at the discretion of the investigator in order to determine eligibility. A subject who does not satisfy all entry requirements that can be assessed during the screening phase will require no further visits and will be identified as a screen failure in the source documents and CRFs.

Re-screening of subjects initially not meeting all selection criteria may be allowed once after consultation with the sponsor.

6.3 Efficacy Assessments Performed

6.3.1 Psoriasis Area and Severity Index (PASI) and Body Surface Area (BSA)

The PASI^[17], a widely used index to express the severity of chronic plaque-type psoriasis, will be assessed at the time points indicated in the schedule of events (Table 1). The PASI is a quantitative rating score for measuring the severity of psoriatic lesions based on area coverage and plaque appearance.

LYC-30937

Clinical Protocol LYC-30937-2003

Issue Date: 30 August 2016

The index combines the assessment of severity of the lesions (erythema, induration/thickness, and desquamation/scaling) and percentage of affected area into a single score ranging from 0 (no disease) to 72 (maximal disease).

The index is calculated as follows (also see Appendix A):

- The subject's body is divided into 4 regions (head, upper extremities, trunk, and lower extremities). Each of these 4 regions is first scored by itself and then all 4 scores are combined into the final PASI.
- For each region, the percent of area of skin involved (0 to 100% BSA), is estimated using the palm (including fingers) and % BSA is totaled for the whole body. Additionally the % BSA in each of the 4 body regions is transformed into a grade from 0 (0%) to 6 (90-100%) for the PASI calculation.
- Within each of the 4 body regions, the severity of chronic plaque-type psoriasis is estimated by the evaluation of 3 clinical signs: erythema (redness), induration (thickness), and desquamation (scaling). Severity parameters are measured on a scale of 0 (none) to 4 (very severe).
- The sum of all 3 severity parameters for each region of skin is then multiplied by the area score for that area and multiplied by a different factor for each region (0.1 for head, 0.2 for upper extremities, 0.3 for trunk and 0.4 for lower extremities).

The investigator will collect the components necessary to calculate the PASI and these components will be entered into the CRF where the PASI score will be calculated. To be eligible for study participation, the subject must have a PASI score of greater than 7 at both the screening visit and the randomization visit, with total BSA involvement of 5-15%, inclusive.

The PASI scoring system is described further in Appendix A.

